**FIGURE OUTPUT CONVENTIONS**

- Figures should be provided in RTF files using the SAS Output Delivery System (ODS), as Computer Graphics Metafile (CGM) formatted graphical output generated by SAS.
- The CGM file itself should contain the title or footer.
- The image should be clear and of high quality when viewed in the Word document, and when printed.
- In general, boxes around the figures should be used.

**FOOTNOTE INFORMATION**

Footers should be defined as follows:

- A continuous line of underscores (‘\_’) will follow the body of the table or listing prior to any footnotes at the bottom of the page
- Table footnotes should be defined using compute statements in the proc report, and should appear directly after the body of the table
- The program path and name and version number (if applicable) should appear as footnote 1 at the bottom of the page
- The date/time stamp should appear as footnote 2 at the bottom of the page
- Footnotes should be left-aligned.
- Footnotes should be in sentence case.
- Only “typewriter” symbols are permitted – eg “\*”, “\$”, “#”, “@”, “&” and “+”.
- The choice of footnote symbols should be consistent. E.g. if you have the footnote “# indicates last observation carried forward” for one table, the same symbol and footnote should indicate LOCF for all tables.
- If text wraps across more than one line (for a note), the first letter for all lines of text after the first one will be indented to align beneath the first letter of the text in the first line.
- The page identification in the format Page X of Y (where Y is the total number of pages for the output) should appear in the first footnote, right aligned

Ordering of footnotes should be as follows:

- 1.) Source data listing reference, if necessary

Version Number: 1.7  
 Version Date: 21Mar2018

- 2.) Abbreviations and definitions
- 3.) Formulae
- 4.) P-value significance footnote
- 5.) Symbols
- 6.) Specific notes

- Common notes from table to table should appear in the same order.
- The symbols should appear in the same order as what they are defined in the table or listing, from left to right.

**PROGRAMMING INSTRUCTIONS**

Programming instructions must appear in blue font at the end of each table or listing shell. Programming instructions, where necessary, should follow the table or listing shells in blue font, beginning with the words “Programming Note” followed by a colon. These include notes on the output, reminders of how to handle missing values, repeat shells for similar tables etc.

**Dates & Times**

Depending on data available, dates and times will take the form yyyy-mm-ddThh:mm:ss.

**Presentation of Treatment Groups**

For outputs, treatment groups will be represented as follows and in that order:

Treatment Group	For Tables and Graphs	For Listings
Placebo	Placebo	Placebo
Bempedoic Acid 180 mg	Bempedoic Acid 180 mg	Bempedoic Acid 180 mg
Not Randomized	Not Randomized	Not Randomized

**Presentation of Visits**

For outputs, visits will be represented as follows and in that order:

Long Name (default)	Short Name
Week -5 (Visit S1)	W-5 (VS1)
Week -4 (Visit S2)	W-4 (VS2)
Week -1 (Visit S3)	W-2 (VS3)

Version Number: 1.7  
 Version Date: 21Mar2018

Long Name (default)	Short Name
Week 0 (Visit T1)	W0 (VT1)
Week 4 (Visit T2)	W4 (VT2)
Week 8 (Visit T3)	W8 (VT3)
Week 12 (Visit T4)	W12 (VT4)
Week 24 (Visit T5)	W24 (VT5)

Listings

All listings will be ordered by the following (unless otherwise indicated in the template):

- randomized treatment
- center-subject ID,
- date (where applicable),
- For listings where non-randomized subjects are included, these will appear in a category after the randomized treatment groups labeled 'Not Randomized'.

Version Number: 1.7  
 Version Date: 21Mar2018

## APPENDIX 2. PARTIAL DATE CONVENTIONS

Imputed dates will NOT be presented in the listings.

Algorithm for Treatment Emergence of Adverse Events:

START DATE	ACTION
Known and AESTART=study med start date	If AEPRIOR=Y then not TEAE If AEPRIOR=N then TEAE
Known and AESTART>or < study med start date	If start date < study med start date, then not TEAE If start date > study med start date and <=study med end date + 30 , then TEAE
Partial	If AEPRIOR=Y then not TEAE Otherwise, If Impute 1 st of month if date is missing; impute 1 st of Jan if both date and month are missing. If resulting imputed start date is prior to study med start date, set as study med start date. If imputed start date is <= study med end date + 30 days, then TEAE; otherwise NOT TEAE
Missing	If AEPRIOR=Y then not TEAE Otherwise, Assumed TEAE

Algorithm for Prior / Concomitant Medications:

Please note that the study med start date is the double-blind med start date.

START DATE	STOP DATE	ACTION
Known	Known	If stop date < study med start date, assign as prior If stop date >= study med start date and start date <= end of treatment, assign as concomitant If stop date >= study med start date and start date > end of treatment, assign as post study

START DATE	STOP DATE	ACTION
	Partial	Impute stop date as latest possible date (i.e. last day of month if day unknown or 31 st December if day and month are unknown), then: If stop date < study med start date, assign as prior If stop date >= study med start date and start date <= end of treatment, assign as concomitant If stop date >= study med start date and start date > end of treatment, assign as post treatment
	Missing	If stop date is missing could never be assumed a prior medication If start date <= end of treatment, assign as concomitant If start date > end of treatment, assign as post treatment
Partial	Known	Impute start date as earliest possible date (i.e. first day of month if day unknown or 1 st January if day and month are unknown), then: If stop date < study med start date, assign as prior If stop date >= study med start date and start date <= end of treatment, assign as concomitant If stop date >= study med start date and start date > end of treatment, assign as post treatment
	Partial	Impute start date as earliest possible date (i.e. first day of month if day unknown or 1 st January if day and month are unknown) and impute stop date as latest possible date (i.e. last day of month if day unknown or 31 st December if day and month are unknown), then: If stop date < study med start date, assign as prior If stop date >= study med start date and start date <= end of treatment, assign as concomitant If stop date >= study med start date and start date > end of treatment, assign as post treatment
	Missing	Impute start date as earliest possible date (i.e. first day of month if day unknown or 1 st January if day and month are unknown), then: If stop date is missing could never be assumed a prior medication If start date <= end of treatment, assign as concomitant If start date > end of treatment, assign as post treatment
Missing	Known	If stop date < study med start date, assign as prior If stop date >= study med start date, assign as concomitant Cannot be assigned as 'post treatment'
	Partial	Impute stop date as latest possible date (i.e. last day of month if day unknown or 31 st December if day and month are unknown), then: If stop date < study med start date, assign as prior If stop date >= study med start date, assign as concomitant Cannot be assigned as 'post treatment'

Version Number: 1.7  
 Version Date: 21Mar2018

START DATE	STOP DATE	ACTION
	Missing	Assign as concomitant

---

[REDACTED]

Version Number: 1.7  
Version Date: 21Mar2018

[REDACTED]

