10.2. Adverse and Serious Adverse Events

10.2.1. Definition of Adverse Event

An AE is any untoward medical occurrence in a clinical investigation patient administered a pharmaceutical product, including control, and which does not necessarily have a causal relationship with treatment.

An AE can be:

- Any unfavorable and unintended sign (including an abnormal laboratory finding), symptom, or disease temporally associated with the use of a medicinal product, whether or not considered related to the medicinal product
- Any new disease or exacerbation of an existing disease
- Any deterioration in nonprotocol-required measurements of laboratory value or other clinical test (eg, ECG or x-ray) that results in symptoms, a change in treatment, or discontinuation from study drug
- TEAEs are defined as AEs that begin or worsen after the first dose of study drug
- Adverse drug reaction (ADR; see [Section 10.2.2](#))

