10.2.3. Reporting

All AEs occurring during the course of the study (starting from signing informed consent to study completion or discontinuation) will be collected on the AE eCRF. Patients should be instructed to report any AE that they experience to the Investigator through 30 days following the last dose of study drug. Beginning with Visit S2 (Week -4), Investigators should make an assessment for AEs at each visit and record the event on the appropriate AE eCRF. Any SAE that occurs from the time of ICF through 30 days following the last dose of study drug should be reported to the Sponsor per [Section 10.2.7.4](#).

Wherever possible, a specific disease or syndrome rather than individual associated signs and symptoms should be identified by the Investigator and recorded on the eCRF. However, if an observed or reported sign or symptom is not considered a component of a specific disease or syndrome by the Investigator, it should be recorded as a separate AE on the eCRF. Additionally, the condition that led to a medical or surgical procedure (eg, surgery, endoscopy, tooth extraction, transfusion) should be recorded as an AE, not the procedure.

Any medical condition already present at screening or baseline should not be reported as an AE unless the medical condition or signs or symptoms present at baseline changes in severity or seriousness at any time during the study. In this case, it should be reported as an AE.

Clinically significant abnormal laboratory or other examination (eg, ECG) findings that are detected during the study or are present at baseline and significantly worsen during the study should be reported as AEs. The Investigator will exercise his or her medical and scientific judgment in deciding whether an abnormal laboratory finding or other abnormal assessment is clinically significant. Significant abnormal laboratory values occurring during the clinical study will be followed until repeat tests return to normal, stabilize, or are no longer clinically significant. Any abnormal test that is determined to be an error does not require reporting as an AE.

Each AE is to be evaluated for duration, severity, seriousness, and causal relationship to the investigational drug. For each AE, the following information will be recorded:

- Description of the event (eg, headache)
- Date of onset
- Date of resolution (or that the event is continuing)
- Action taken as a result of the event
- Seriousness of the event
- Severity of the event

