10.2.7. Treatment-Emergent Adverse Event

TEAE are defined as AEs that begin or worsen after the first dose of study drug.

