### 19.1. ADVERSE EVENTS

Adverse Events (AEs) will be coded using MedDRA, Version 20.1.

Treatment emergent adverse events (TEAEs) are defined as AEs that started or worsened in severity after the first dose of IMP (double-blind study medication) and prior to the last dose date of double-blind study medication + 30 days. AEs that occurred on day 1 will be only be determined as TEAE if the site indicated it occurred after first dose on the AE CRF.

See [Appendix 2](#) for handling of partial dates for AEs. In the case where it is not possible to define an AE as treatment emergent or not, the AE will be classified by the worst case, i.e. treatment emergent.

An overall summary of number of subjects within each of the categories described in the subsection below, will be provided as specified in the templates. Listings will include TEAEs and Non-TEAEs.

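### For adverse events with a known onset before first double-blind dose, or flagged AEPRIOR=Y, SAP Appendix 2 has no test for worsening and so contradicts the TEAE definition

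*SAP*

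**What the plan says.** The definition appears in three places and is consistent on this point. Protocol 10.2.7 states: "TEAE are defined as AEs that begin or worsen after the first dose of study drug". Protocol 10.2.1 repeats it. SAP 19.1 says that TEAEs "are defined as AEs that started or worsened in severity after the first dose of IMP (double-blind study medication") and sets an end limit of 30 days after the last dose.

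SAP Appendix 2 then supplies a table headed "Algorithm for Treatment Emergence of Adverse Events". Its rows cover known, partial and missing start dates, and they use only the start date, the AEPRIOR flag and the 30-day window. For a known date earlier than the start of double-blind drug the rule is "If start date < study med start date, then not TEAE". AEPRIOR=Y gives the same result in the rows for an onset on the first-dose date, a partial date and a missing date. For a partial date without AEPRIOR=Y the rule leans the other way: "If resulting imputed start date is prior to study med start date, set as study med start date". A missing date without AEPRIOR=Y is taken as a TEAE.

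On collection, protocol 10.2.3 has AEs recorded "starting from signing informed consent to study completion or discontinuation", so events from screening and the 4-week placebo run-in are in the database. For each AE that section lists an onset date, a resolution date and a severity, but no date on which severity changed.

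**The concern.** An AE can begin in the run-in, be mild enough for the patient to be randomized, and become more severe on double-blind drug. The definition was written to capture this case, but the classification table has no branch for it. If a site raises the severity on the existing record, the onset stays before first dose and the table removes the event. If another site opens a new record for the same course of symptoms, the event counts. Classification would then depend on site habit.

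TEAE status governs the summaries by system organ class and preferred term, by maximum severity and by relationship (SAP 19.1.1), TEAEs leading to discontinuation (19.1.2), serious TEAEs (19.1.3), and the DMC tables in Appendix 3, including the one for treatment-emergent AESIs. The AESI list in Appendix 5 includes myalgia, muscle spasms and pain in extremity. These matter in a statin-intolerant population, in whom such symptoms may well be present before dosing.

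**Working it through.** The plan gives no figure to reproduce, so the check runs both rules on the same hypothetical event.

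Inputs. First double-blind dose is Day 1. Last dose is taken as Day 168, an assumption for illustration, so the window ends at 168 + 30 = Day 198. The event begins on Day -10, in the run-in, and either stays the same or worsens on Day 30, which lies inside the window. AEPRIOR is read as the CRF flag for onset before first dose, since the SAP does not define it.

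Rule A (SAP 19.1 text): TEAE if the onset or the worsening falls after Day 1 and before Day 198.
Rule B (Appendix 2): the row for the type of start date, with AEPRIOR where that row uses it.

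| Start date | AEPRIOR | Worsens Day 30? | Rule A | Rule B |
|---|---|---|---|---|
| Known, Day -10 | any | no | not TEAE | not TEAE |
| Known, Day -10 | any | yes | **TEAE** | **not TEAE** |
| Partial or missing | Y | no | not TEAE | not TEAE |
| Partial or missing | Y | yes | **TEAE** | **not TEAE** |
| Partial or missing | N or blank | no | not TEAE | TEAE |
| Partial or missing | N or blank | yes | TEAE | TEAE |

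The bold rows are the conflict. With a known date the worsened event is lost whatever AEPRIOR says. With a partial or missing date it is lost only when AEPRIOR=Y.

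The fifth row goes the other way: an event that truly began before dosing and never worsened becomes a TEAE. That agrees with SAP 19.1, which sends unclassifiable events to the treatment-emergent side. Taken together, though, Appendix 2 can count an unworsened event with a vague date and omit a worsened event with an exact one.

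A side result concerns the end of the window. SAP 19.1 requires the event to fall before last dose + 30 days, while Appendix 2 includes that day. An onset on Day 198 is a TEAE under Appendix 2 and not under 19.1.

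**The case against.** The strongest reply has four parts.

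- **Status of Appendix 2.** The appendix is titled as a partial-date convention, and SAP 19.1 cites it only for partial dates. A reader may take the 19.1 text as controlling. That is fair, and nothing in the SAP proves that the table will override the text. But the table has explicit known-date rows under a general heading, and no sentence says which prevails.
- **Other provisions narrow the gap.** Protocol 10.2.3 makes a condition present at baseline reportable as an AE once its severity or seriousness changes, and the natural onset for that record is the date of change. Protocol 7.5 keeps patients with placebo-related run-in AEs from randomization, and 8.3.4 makes intolerable side effects, musculoskeletal pain among them, run-in failures. This stands in part. It does not cover an unrelated, tolerable AE already logged in the run-in, and 10.2.3 states neither that a new record is opened nor that onset means the date of worsening.
- **The answer may lie elsewhere.** The protocol refers to CRF completion guidelines (15.3) and a Study Operations Manual (8.3), which are not available here. If they require a new record for each worsening, Appendix 2 classifies that record correctly.
- **The events are not lost.** Listings include non-TEAEs. The laboratory abnormality summaries in SAP 19.4 do not depend on TEAE status, and the text of 19.1.5 on muscle events is not limited to TEAEs. This stands, and it limits the consequence to the summaries that depend on TEAE status.

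A reader might infer that the table discards every AE that began before dosing. It does not, as the last two rows of the comparison show. A reader might also infer that muscle harm on active drug will be understated. The documents give no count of such events and no evidence on how they would fall by arm.

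**Conclusion.** The contradiction is real and specific. For AEs with a known start date before first double-blind dose, and for AEs flagged AEPRIOR=Y, Appendix 2 returns not treatment-emergent without considering worsening, while SAP 19.1 and protocol 10.2.1 and 10.2.7 count worsening. This is a stated rule that gives the wrong answer under the plan's own definition, not just missing detail.

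The practical effect falls on AEs first logged during screening or run-in, compatible with randomization, that worsen on double-blind drug and are updated on the same record. It rests on two assumptions: that programmers follow the table as written, and that no unseen guideline requires a new record. The size of the effect and its direction between arms cannot be determined from the documents. The efficacy analyses are untouched.

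**What to change.** Two changes are needed together, because protocol 10.2.3 lists no date of severity change and an algorithm line alone may not be programmable.

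1. **Recording.** State in the protocol or the CRF completion guidelines that an increase in severity after first double-blind dose is entered as a new AE record, with the date of worsening as its start date. Alternatively, collect the date of severity change on the existing record.
2. **Algorithm.** In Appendix 2, add to the row for known dates before first dose and to each AEPRIOR=Y row that an AE whose severity increased after first dose and by last dose + 30 days is a TEAE. In the same edit, settle whether the final day of the window is included, so that the table and SAP 19.1 agree, and say that the 19.1 definition prevails if they differ.

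The cost is one recording instruction, or one added CRF field, plus a short clause in a few table rows. No visit, assessment or clinical rule changes.

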### APPENDIX 3. LIST OF DMC TABLES, LISTINGS AND FIGURES

#### TABLES

- 14.1.1.1 Patient Disposition – All Patients
- 14.1.2.1a Demographic and Other Baseline Characteristics – Full Analysis Set
- 14.1.3.1 Medical/Surgical History – Full Analysis Set
- 14.1.3.3 Targeted Cardiovascular History/Risk Factors – Full Analysis Set
- 14.1.5.1 Study Drug Compliance – Safety Analysis Set
- 14.3.1.1 Overview of Treatment-Emergent Adverse Events – Safety Analysis Set
- 14.3.1.2 Treatment-Emergent Adverse Events by Maximum Severity, System Organ Class and Preferred Term – Safety Analysis Set
- 14.3.1.3 Serious Treatment-Emergent Adverse Events by Maximum Severity, System Organ Class and Preferred Term – Safety Analysis Set
- 14.3.1.4 Related Treatment-Emergent Adverse Events by Maximum Severity, System Organ Class and Preferred Term – Safety Analysis Set
- 14.3.1.5 Related Serious Treatment-Emergent Adverse Events by Maximum Severity, System Organ Class and Preferred Term – Safety Analysis Set
- 14.3.1.6 Treatment-Emergent Adverse Events That Led to Discontinuation of Study Drug by Maximum Severity, System Organ Class and Preferred Term – Safety Analysis Set
- 14.3.1.8 Treatment-Emergent AESIs by Maximum Severity, System Organ Class and Preferred Term – Safety Analysis Set
- 14.3.1.15 Investigator-reported Major Cardiac Events (MACE) by Event Type – Safety Analysis Set
- 14.3.1.16 Adjudicated Major Cardiac Events (MACE) by Event Type – Safety Analysis Set
- 14.3.2.8 Laboratory Parameters of Interest: Observed and Change from Baseline – Safety Analysis Set
- 14.3.2.9 Laboratory Parameters of Interest: Laboratory Abnormalities – Safety Analysis Set

Version Number: 1.7  
 Version Date: 21Mar2018

14.3.2.10 Quantitative Clinical Laboratory Evaluations: Lipids – Safety Analysis Set (note that this table is produced for DMC only)

## FIGURES

14.3.1 Boxplots of Hematology Parameters

14.3.2 Boxplots of Chemistry Parameters

The next 2 listings will be created at the same time frame as DMC TLFs above. However, these 2 listings will be sent to Esperion Team only for monitoring thresholds for protocol deviations and for evaluable patients, but not sent to DMC members.

Listing 16.2.3 Patient Inclusion per Analysis Population – All Screened Patients

Listing 16.2.4 Screen Failures – All Screened Patients (note that this listing is produced for DMC only)

---

Version Number: 1.7  
Version Date: 21Mar2018

**APPENDIX 4. DETAILS OF MULTIPLE IMPUTATION METHOD**

Missing Week 12 values will be imputed based on baseline values. The following table details the possible cohorts and which cohorts will be used for imputation. Missing Week 24 values will be imputed in the same way.

	Treatment	Week 12 Value	On Treatment at Week 12	Imputation Cohort(s)
1	Placebo	Missing	Yes	Cohort 5: Placebo patients with non-missing Week 12
2	BA	Missing	Yes	Cohorts 6 and 8 BA patients with non-missing Week 12
3	placebo	Missing	No	Cohort 5: Placebo patients with non-missing Week 12
4	BA	Missing	No	Cohorts 5 and 7 Placebo patients with non-missing Week 12 and not on treatment
5	placebo	Non-missing	Yes	
6	BA	Non-missing	Yes	
7	placebo	Non-missing	No	
8	BA	Non-missing	No	

Imputation code for Cohorts 1-3.

```
proc mi;
where cohort in(1,2,3,5,6,8);
class trt01pn strata;
monotone regression;
var trt01pn strata base aval;
run;
```

Imputation code for Cohort 4.

```
proc mi;
where cohort in(4,5,7);
class strata;
monotone regression;
var base strata aval;
run;
```

[figure not shown]
Version Number: 1.7  
 Version Date: 21Mar2018

Two hundred imputed datasets will be created, with results from the analysis of each imputed dataset (ANCOVA) combined using Rubin’s method.

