8.3.5. Treatment Week 4 (Visit T2; Day 29 ±3 days)

Patients will undergo the following assessments and procedures at Week 4 (Visit T2):

1. Concomitant medication review (ongoing)
2. Assess AEs, SAEs, and potential clinical endpoints

3. Weight
4. Vital signs
5. Central clinical laboratory evaluations:
 - Hematology, blood chemistry, and urinalysis
 - Basic fasting lipids (TC, calculated LDL-C, HDL-C, non-HDL-C, and TG)
 - PK Sample prior to dose
6. Return of study drug; assessment and recording of dosing adherence
7. Re-dispense IMP container from Visit T1 to patient for continued dosing and provide dosing and storage instruction.

Note: If the patient discontinues at any scheduled visit after T1, or between study visits, please proceed to [Section 8.4.1](#) for detailed instructions.

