### 3. STUDY DESIGN

#### 3.1. GENERAL DESCRIPTION

This is a Phase 3, randomized, double-blind, placebo-controlled, parallel group multicenter study that will be conducted at approximately 71 clinical sites in North America. Screening Week -5 (Visit S1) will be approximately 5 weeks prior to randomization. Eligible patients will return to the clinical site at Week -4 (Visit S2) to initiate administration of single-blind (patient only) placebo study drug. Eligible patients will return at Week -1 (Visit S3) for lipid and safety laboratories and an assessment of tolerability and study drug adherence. Approximately 300 patients with a history of statin intolerance (SI) will be stratified based on patient type (primary prevention; secondary prevention) and randomized at Week 0 (Visit T1) in a 2:1 ratio to receive either bempedoic acid 180 mg (n = 200) or matching placebo (n = 100) once daily for 24 weeks. Randomized patients will return for clinic visits at Week 4 (Visit T2), Week 12 (Visit T4), and Week 24 (Visit T5). A phone visit will occur at Week 8 (Visit T3).

Figure A 1002-046 Study Design

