# 7. STATISTICAL CONSIDERATIONS

## 7.1. SAMPLE SIZE

The primary efficacy endpoint for this study is the percent change from baseline to Week 12 in LDL-C.

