## 7.5. MULTIPLE COMPARISONS/ MULTIPLICITY

In terms of controlling the overall Type I error rate, a gatekeeping or stepdown approach will be used to test the primary efficacy endpoint and then specific secondary efficacy endpoints sequentially in order to preserve the study-wise Type I error rate. The sequence for the stepdown procedure in this study is as follows:

1. Test the primary efficacy endpoint: percent change from baseline to Week 12 in LDL-C
2. Test the percent change from baseline to Week 24 in LDL-C
3. Test the percent change from baseline to Week 12 in non-HDL-C
4. Test the percent change from baseline to Week 12 in TC
5. Test the percent change from baseline to Week 12 in apoB
6. Test the percent change from baseline to Week 12 in hsCRP

In this hierarchical testing structure, each hypothesis is tested at a significance level of 0.05, two-sided. Statistical significance at each step is required in order to test the next hypothesis. If the primary endpoint meets the criteria for statistical significance, then the percent change from

[REDACTED]

[figure not shown]
Version Number: 1.7  
 Version Date: 21Mar2018

[REDACTED]

baseline to Week 24 in LDL-C will be tested; and so forth.

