## 18. EFFICACY OUTCOMES

### 18.1. PRIMARY EFFICACY

#### 18.1.1. PRIMARY EFFICACY VARIABLE & DERIVATION

The primary efficacy endpoint is the percent change from baseline to Week 12 in LDL-C. Baseline LDL-C is defined as the mean of the LDL-C values from Week -1 (Visit S3) and predose Day 1/Week 0 (Visit T1).

In cases where triglycerides (TG) is >400 mg/dL or LDL-C is <=50 mg/dL, a measured LDL (LDL-M) will be used instead of LDL-C for the analysis of that time point. If both values are available, the LDL-M will be used.

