**18.1.3. MISSING DATA METHODS FOR PRIMARY EFFICACY VARIABLE**

For the primary endpoint of percent change from baseline to Week 12 in LDL-C values, a pattern mixture model (PMM) will be used to specify different imputation strategies depending on whether the patient is still on study treatment. Patients with missing lipid data at Week 12 who are no longer taking study treatment (defined by date of last dose of study medication is < Week 12 lab assessment date -7) can be assumed to no longer be benefitting from study medication, and their missing value(s) can be assumed to be similar to those in placebo group who remained on study and have data. To account for uncertainty, missing values will be imputed using multiple imputation via a regression based model including stratification and baseline data from placebo subjects only. In this imputation model, treatment group will not be included as a factor.

Patients with missing lipid data at Week 12 who are still taking study treatment (date of last dose of study medication is ≥ Week 12 lab assessment date -7) can be assumed to continue to benefit from study medication, and their missing value(s) can be assumed to be similar to those who remain on study treatment and have data and as a result, lipid values will be imputed based on the observed values in their randomized treatment group at Week 12. To account for uncertainty, missing values will be imputed using multiple imputation via a regression based model including treatment, stratification and baseline value.

Imputed datasets will be analyzed using the same ANCOVA model with treatment and stratification as factors and baseline LDL-C as a covariate described in [section 18.1.2](#). Approximately 200 imputed datasets will be created, with results from the analysis of each imputed dataset combined using Rubin’s method. The least squares mean (LSM) and standard error (SE) will be provided for both treatment groups, along with the placebo-corrected LSM, its 95% confidence interval (CI) and associated p-value. To account for possibility of unequal variances between the groups, the ANCOVA model will be implemented within mixed model framework where <repeated/group=> option will be used to allow separate estimation of residual variance between the groups.

Further information on the multiple imputation method is presented in [Appendix 4](#).

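### The imputation model for missing Week 12 and Week 24 lipids omits the patient's own earlier on-study values, which costs a little precision and leaves the estimate open to bias if missingness depends on early response differently by arm

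*SAP*

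**What the plan says.** SAP Appendix 4 opens with "Missing Week 12 values will be imputed based on baseline values" and applies the same method to Week 24. Read alone, that sentence suggests a baseline-only model, but the PROC MI call for cohorts 1 to 3 has "var trt01pn strata base aval", so treatment and stratum are also predictors. SAP 18.1.3 agrees: for patients still on treatment, "missing values will be imputed using multiple imputation via a regression based model including treatment, stratification and baseline value". No value measured after randomization enters as a predictor.

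Cohorts 1 and 2 are placebo and active patients still on treatment with a missing value. Cohort 3 is placebo patients off treatment. Active patients off treatment (cohort 4) have a separate call with placebo donors only.

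The earlier values exist. At Week 4, Protocol 8.3.5 collects "Basic fasting lipids (TC, calculated LDL-C, HDL-C, non-HDL-C, and TG"), and Protocol 8.3.7 repeats this panel at Week 12. ApoB and hs-CRP are not scheduled at Week 4 (Protocol Table 2).

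The four sensitivity analyses in SAP 18.2.3 (completer, adjunctive therapy, on-treatment, observed data) impute nothing, so none uses Week 4 to recover a missing Week 12 value.

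**The concern.** A patient's LDL-C at Week 4 on study drug should predict that patient's Week 12 value well, and Week 12 should do the same for Week 24. A model without them assumes that, given treatment, stratum and baseline, missingness says nothing about how the patient was responding. Week 4 is where a failure of that assumption would show.

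The planned sensitivity analyses would not expose it. The observed-data ANCOVA conditions on the same three variables, so its agreement with the primary result is no test of whether missingness tracks early response.

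At stake are the size and precision of the estimated effect for the primary endpoint and for Week 24 LDL-C, which is second in the testing sequence of SAP 7.5.

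**Working it through.** **Inputs from the documents.** 200 active and 100 placebo patients (SAP 3.1); two-sided 0.05 (SAP 7.5); percent change in LDL-C as the outcome (SAP 18.1.1).

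**Inputs not readable in the public text.** SAP 7.1 shows only the sentence naming the endpoint. There is no power figure to reproduce, and no SD, effect or missing rate. The following are assumptions: SD 20 points, effect 15 points, Week 4 to Week 12 correlation given baseline ρ = 0.7 (range 0.5-0.8), and on-treatment missing fraction p of 2%, 5% and 10%.

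**Scale.** The complete-data standard error is 20 × √(1/200 + 1/100) = 2.45 points.

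**Precision, missingness unrelated to response.** The variance is inflated by 1/(1−p) without Week 4 and by ρ² + (1−ρ²)/(1−p) with it.
- p = 5%: 1/0.95 = 1.0526 against 0.49 + 0.51/0.95 = 1.0268; SE ratio √(1.0526/1.0268) = 1.012.
- p = 10%: 1/0.90 = 1.1111 against 0.49 + 0.51/0.90 = 1.0567; SE ratio 1.025.
- Over ρ = 0.5-0.8 the ratio is 1.003-1.007 at 2%, 1.006-1.016 at 5% and 1.013-1.034 at 10%.

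**Bias within an arm.** If patients with missing values are d SDs worse at Week 4 than their arm as a whole, omitting Week 4 shifts the arm mean by p/(1−p) × ρ × d × SD in the favourable direction. Take d = 1.
- Active arm only, SD 20, p = 5%: 0.05/0.95 × 0.7 × 20 = 0.74 points (0.53-0.84 over ρ).
- Active arm only, SD 20, p = 10%: 0.10/0.90 × 0.7 × 20 = 1.56 points (1.11-1.78 over ρ).
- Both arms alike, equal SDs: the shifts cancel.
- Both arms alike, SD 20 active and 28 placebo: the net shift is p/(1−p) × 0.7 × (28 − 20), that is 0.29 points at 5% and 0.62 at 10%, against the drug.

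**Simulation** (200/100, SD 20, effect 15, ρ = 0.7, ANCOVA with group-specific variances, Rubin's rules, 20 imputations, 600 runs per row). Bias is relative to the complete data; negative favours the drug.

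| Missingness | p | Bias without Week 4 | Bias with Week 4 | Mean SE without / with |
|---|---|---|---|---|
| Unrelated | 5% | about 0 | about 0 | 2.524 / 2.491 |
| Unrelated | 10% | about 0 | about 0 | 2.607 / 2.540 |
| Depends on Week 4, both arms | 5%, 10% | about 0 | about 0 | little difference |
| Depends on Week 4, active only | 2% | −0.3 | about 0 | 2.476 / 2.467 |
| Depends on Week 4, active only | 5% | −0.8 | about 0 | 2.510 / 2.489 |
| Depends on Week 4, active only | 10% | −1.5 | about 0 | 2.575 / 2.533 |

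Further runs of the SAP's pooled model gave −0.9 and −1.7 points at 5% and 10% in the active-only case. With SDs of 20 and 28 and dependence in both arms, they gave +0.24 at 5% and +0.44 to +0.65 at 10%.

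With no true effect and active-only dependence (1,500 runs, Monte Carlo error about 0.006), the rejection rate without and with Week 4 was 0.058 and 0.050 at 5% missing, and 0.084 and 0.046 at 10%. Power at an effect of 15 was 1.00 in every scenario.

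**The case against.** The model is prespecified and follows the assumption in Protocol 11.5 that on-treatment missing values resemble observed ones in the same arm. The affected group is narrow. SAP 18.1.3 counts a patient as on treatment only if the last dose falls no more than 7 days before the Week 12 laboratory date. Active patients who stop and have no value get placebo-based imputation, so stopping for intolerance is already handled conservatively. Patients who stop are asked to keep giving fasting lipids (Protocol 8.4), and a non-fasting visit can be rescheduled within 3 days (Protocol 9.2). Post-randomization lipids are masked from patient, site, sponsor and CRO (Protocol 6.3), which makes selection on known response unlikely. On-treatment missing values may therefore be few.

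Most of this stands and is why the point is minor. It does not close the adherence route. Poor adherers stay in the study (Protocol 7.5), and missing doses raises LDL-C on active drug but not on placebo. One rule linking adherence to missed visits can then create arm-differential dependence on Week 4. In a simulation with 15% poor adherers having zero or half effect, a true effect of 20 points and the same missingness rule in both arms, the effect was overstated by 0.2-0.5 points at 5% missing and 0.5-1.0 at 10%. Adding Week 4 removed about 70% of that.

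A reader might infer that the primary analysis is biased in favour of the drug. The documents do not support that. They give no missing rate and no sign that missingness tracks Week 4 response differently by arm, and the direction itself depends on the variances.

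**Conclusion.** The omission is certain from the SAP text and code; its effect on the result is not. The precision loss is about 1% of the standard error at 5% missing and 2-3% at 10% (ρ = 0.7). The exposure to bias is about 0.5-0.9 points at 5% and 1.1-1.8 at 10%, in favour of the drug, and only when dependence on early response is confined to the active arm with SD near 20 and missing patients about 1 SD worse. Under equal dependence and equal variances it is about zero. The size of the estimate is exposed more than the significance of the primary test. The Week 12 to Week 24 part concerns a key secondary endpoint, not the primary analysis.

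Severity: minor. It would matter more if on-treatment missingness were near 10% and related to response differently by arm.

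**What to change.** In SAP Appendix 4 and 18.1.3, for on-treatment patients with missing values (cohorts 1 and 2):

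- Add observed Week 4 LDL-C as a predictor before aval, and Week 12 LDL-C as well for the Week 24 endpoint.
- Add Week 4 TC and Week 4 non-HDL-C for those endpoints. Leave apoB and hs-CRP unchanged.
- Fill missing Week 4 values first by a non-monotone method (for example FCS, or MCMC to a monotone pattern). A patient with Week 4 missing and Week 12 observed breaks the pattern that the present MONOTONE call needs, so extending the variable list is not enough.
- Keep cohort 4 on baseline and stratum with placebo donors. State whether off-treatment placebo patients (cohort 3) follow the same rule as cohort 4; otherwise off-treatment patients in the two arms would be imputed from different information.
- Check whether cohort 8 donors (active, measured off drug) distort the Week 4 to Week 12 slope.

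The cost is one extra imputation step and no new data. The SAP addendum records that the planned analyses are complete, so this would now be a sensitivity analysis labelled post hoc, reported with the number of on-treatment missing values by arm.
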